10.0 Data and Specimen Banking: Not Applicable

10.1. *Data analysis*

Specific Aim 1 (Feasibility; Primary Aim): To demonstrate the feasibility of the PATH intervention in patients with hematologic malignancy undergoing HSCT: Based on prior work, we define feasibility as >75% of enrolled participants who start the intervention completing at least 6 of the

PROTOCOL TITLE: Randomized Trial of a Positive Psychology Intervention for Patients with Hematologic Malignancies Undergoing Hematopoietic Stem Cell Transplantation

9 PP sessions, consistent with metrics used in prior positive psychology feasibility trials^{17, 54} and other behavioral intervention studies.⁸⁵⁻⁸⁷ We will estimate the feasibility using the proportion who meet the criteria, and we will place an exact 95% binomial confidence interval around the proportion. We will assess acceptability using weekly ratings of ease and utility of each exercise (0=very difficult/not helpful; 10=very easy/very helpful). The mean ease and utility of each exercise and overall will be calculated, and will use a threshold of a mean combined score of 7.0/10 for acceptability that was used in prior studies.^{19,57}

Specific Aim 2 (Effects on Patient-Reported Outcomes): To assess the preliminary efficacy of the PATH intervention on psychological (e.g., depression, anxiety, optimism, positive affect), QOL, and functional outcomes compared to the usual care condition: Analyses will begin with descriptive and graphical summaries of the endpoints and evaluation of whether a normality assumption is reasonable for the endpoint or whether transformation is necessary. We will use a Bonferroni correction to address multiple measures and testing. All statistical tests will be two-sided with a liberal alpha level of 0.2 to detect a signal on the impact of the intervention on patient- reported outcomes. We will summarize participants' baseline characteristics using descriptive statistics (e.g., mean) for continuous variables and proportions for categorical variables.

To examine the immediate impact of the intervention on happiness and optimism, we will use generalized estimating equations (GEE) to determine the immediate impact of a PP session on optimism and happiness. The GEE model will allow us to account for the repeated observations on subjects from the different exercises.

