Specific Aim 3 (Effects on Health Behaviors): To examine the impact of the PATH intervention on behavioral outcomes (e.g., medication adherence, physical activity) compared to those in the usual care condition: We will initially compare physical activity (# of steps/day) at 9- and 18-weeks between the intervention and control groups using a Wilcoxon rank sum test, given that the distribution of the number of steps will likely be skewed. We will also use random effects regression models with a random intercept for each participant to compare between-group differences in change over time in physical activity and medication adherence. All statistical tests will be two tailed, with $p < 0.05$ considered significant.

Missing Data: We will also use the intention-to-treat principle with all randomized participants and conducting sensitivity analyses to explore various assumptions about missing data. If source of the missing data appear to be missing at random, the linear mixed effects models described above provide an unbiased estimate of the regression coefficients. However, if we find that participants do not complete the study because of disease worsening, suggesting missing data are not random, we will employ pattern mixture modeling or joint modeling approaches⁹⁰ to handle incomplete data, and perform sensitivity analysis⁹¹ to assess the impact of missing data. In addition to the intention-to-treat analysis, we will also estimate the group differences in the completers to estimate the per protocol group difference.

10.2. Sample Size Calculation & Power Analysis:

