Based on prior trials in this population,⁹² we anticipate 15% of enrolled participants will be unable to complete the intervention due to medical complications and mortality. Hence, we will enroll 70 participants (35 in the [PATH] PP arm) to target having at least 30 PP participants who complete the intervention. For our primary aim (feasibility), in prior trials, approximately 80% of participants have completed 6 of 9 PP exercises.⁹ Using the same rate, with 30 PATH participants, we will have 95% power (two-sided $\alpha = .05$, binomial proportion test) to demonstrate that the proportion who complete > 6 of 9 PP sessions is larger than 50% (i.e., a majority). For acceptability, using this sample size, we will have 95% power to detect a true mean score of > 7.0 based on prior work (in which mean utility scores were 7.8 ± 1.8).¹² This pilot RCT is not designed to definitively detect significant ($p < .05$) group differences in psychological, QOL, or behavioral outcomes (and we would need between-group effect size differences of $d = .74$ to be powered at 80% to detect significant differences). However, this sample of 30 completers in each group will allow us to preliminarily explore the impact of PATH on clinical outcomes and make tentative estimations of effect sizes.

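### Aim 3 analyses physical activity in two ways, adds medication adherence, and calls each p<0.05 significant with no deciding analysis and no stated correction

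*Combined protocol and SAP*

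**What the plan says.** Section 10.1, Specific Aim 3, contains two analyses of activity. The first: "We will initially compare physical activity (# of steps/day) at 9- and 18-weeks between the intervention and control groups", by Wilcoxon rank sum test because skew is expected. The second is a set of random-intercept regression models, used "to compare between-group differences in change over time in physical activity and medication adherence". The model's activity metric is not named. The paragraph closes with "All statistical tests will be two tailed, with" p<0.05 counted as significant. It gives no order of importance, no deciding time point and no correction.

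The surrounding text matters in four ways:

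- **Multiplicity.** Under Aim 2 the same section says "We will use a Bonferroni correction to address multiple measures and testing", next to an alpha of 0.2 for patient-reported outcomes. The family is not defined, and the sentence is not repeated for Aim 3.
- **Status.** Section 10.2 says "This pilot RCT is not designed to definitively detect significant" group differences at p<.05, and names behavioural outcomes among those covered. Section 8.0 lists activity and adherence as secondary endpoints.
- **Metric.** Section 9.4 (Health Behaviors) makes minutes/day of light activity the primary activity measure, alongside sedentary leisure time. Aim 3 uses steps/day.
- **Schedule.** Section 9.4 has the accelerometer worn at baseline, Week 9 and Week 18, and Aim 3 compares steps at both follow-ups. Table 4 in section 9.6 marks the accelerometer at baseline and Week 9 only and ends MEMS at Week 9. Section 9.7 has both devices returned at Week 9.

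**The concern.** Aim 3 carries a directional hypothesis (section 1.2): behaviour improves under PATH. As written, that hypothesis could be reported as supported if any one of several tests falls below 0.05, each at the full 5%.

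The two activity analyses also estimate different quantities. The Wilcoxon test compares levels at a visit, while the model compares change from baseline. One may pass and the other fail on the same data, and the plan does not say which is then the result.

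The unnamed model metric leaves one more choice open after the data are seen. What is at stake is how the behavioural findings are labelled and carried into the planned efficacy trial. The feasibility conclusion is not affected.

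**Working it through.** **1. The plan's own figure.** Section 10.2 gives d = 0.74 for 80% power at two-sided 0.05 with 30 completers per arm (35 × 0.85 = 29.75). For a two-sample t test the noncentrality is d√(n/2) = 0.74 × √15 = 2.87 on 58 degrees of freedom, so power is 80.5%. The smallest d giving 80% power is 0.736. The figure reproduces, and it applies to one test at 0.05.

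**2. Number of tests.** The plan does not list them, so this is a range:

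- Two: Wilcoxon and model on activity at Week 9 only (Table 4 governs).
- Four: both methods at Weeks 9 and 18 (section 9.4 and Aim 3 govern).
- Six or eight: the four activity tests plus the model on MEMS at two visits, then also on MARS-5 at two visits.

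Section 8.0 also lists the SSEQ under adherence, but section 9.4 describes it as a social-support measure, so it is not counted. I take the model to have the time-by-group form that section 10.1 sets out for Aim 2.

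**3. Chance of at least one p<0.05 with no effect.** The reference for k independent tests is 1 − 0.95^k. The tests are correlated, so trials were also simulated: 20,000 runs, 30 per arm, complete data, log-normal steps with log SD 0.6, within-person correlation 0.3 to 0.85, and correlation between outcomes 0 or 0.3. All of these settings are assumptions.

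| Tests | Independent | Simulated |
|---|---|---|
| 2 activity, Week 9 | 9.8% | 8.7-9.6% |
| 4 activity, both visits | 18.5% | 15.5-16.6% |
| 4: activity, MEMS and MARS-5, Week 9 | 18.5% | 17.0-18.3% |
| 6: activity + MEMS, both visits | 26.5% | 22.9-23.9% |
| 8: + MARS-5, both visits | 33.7% | 29.1-30.8% |

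Against a nominal 5%, this is roughly a two- to six-fold inflation.

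**4. Why the two activity tests disagree.** On the log scale, with SD σ and within-person correlation ρ, the between-arm difference in follow-up means has variance 2σ²/n. The difference in mean change has variance 4σ²(1−ρ)/n. The correlation between the two contrasts is √((1−ρ)/2), which is √0.35 = 0.59 at ρ = 0.3 and √0.075 = 0.27 at ρ = 0.85. The two analyses therefore share only part of their information, and less as ρ rises.

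**5. How often they disagree at Week 9.**

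- No effect: 8-9% of trials.
- Assumed shift of 0.5 SD on the log scale: 31-47% for ρ from 0.3 to 0.85. Wilcoxon power stays near 45%, while model power on raw steps rises from about 32% to 87%.
- Assumed 1.3-fold effect, which is ln(1.3)/0.6 = 0.44 SD: about 29% at ρ = 0.3 to 50% at ρ = 0.8.

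Under these effects the two estimates point the same way in about 95-99% of the discordant trials. Both tests significant in opposite directions occurred in essentially none.

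**The case against.** The strongest reply is that this is a feasibility pilot. Section 10.2 limits behavioural results to preliminary exploration and tentative effect sizes. Section 10.1, although under Aim 2, plans Cohen's d for the secondary outcomes at 9 and 18 weeks. No go/no-go rule rests on an Aim 3 p-value. The wording can also be read as a simple first comparison followed by modelling, and section 9.4 does rank the activity metrics. This stands as a reason to keep the severity modest. It does not settle which result counts, because the paragraph still labels p<0.05 significant and the ranked metric is not the one its first test uses.

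A second reply is that Bonferroni already covers Aim 3. The sentence belongs to the Aim 2 paragraph and its different alpha. Even if it was meant to extend further, it cannot be applied without a defined family.

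Stronger readings are tempting, and the documents do not support them:

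- *False positives are likely.* Every figure above is below one half.
- *About 11 tests, with a 37% error chance.* That count treats light activity, sedentary time, MEMS and MARS-5 as each tested separately. Aim 3 names only steps/day, physical activity and medication adherence, and Table 4 would remove the Week-18 device tests.
- *The two tests contradict each other on one outcome.* The model's metric is not stated, so a shared outcome is not established. The disagreement is nearly always one p-value crossing 0.05 with both estimates on the same side.
- *Section 10.2 disowns the threshold.* It says the trial is not designed to detect such differences definitively. That sits awkwardly with a significance label but does not withdraw it.

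**Conclusion.** The concern holds in a limited form. Aim 3 sets a per-test 5% rule over several behavioural tests without a deciding analysis or a stated correction. With no effect, the chance of at least one significant activity result is about 9% if device data stop at Week 9, and 15-17% if both visits are tested. It rises to about 31% with MEMS and MARS-5 at both visits. With a moderate true effect, the two activity analyses give different significance calls in roughly 29-50% of trials, mostly a matter of precision and not of direction.

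These sizes rest on assumed test counts, correlations, log-normal steps, effect sizes and complete data, none of which the documents give. The absence of a decision rule, and the mismatches of metric and schedule, can be read directly from the text and do not depend on the simulation. Severity is modest: these are preliminary secondary comparisons, and the primary feasibility aim is untouched.

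**What to change.** 1. Reconcile the activity metric: light-activity minutes/day in section 9.4 or steps/day in Aim 3. State which one the model uses.
2. Reconcile the Week-18 device schedule: section 9.4 and Aim 3 against Table 4 and section 9.7.
3. Name one deciding analysis per behaviour outcome at one time point. One option is the model's Week-9 time-by-group contrast on the reconciled metric, log-transformed if skewed.
4. Make the Wilcoxon test a sensitivity analysis.
5. Report all other measures and time points as estimates with confidence intervals and no significance label, in line with section 10.2.
6. State whether the Bonferroni sentence covers Aim 3 and, if so, over which family.

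The cost is SAP wording only. The downside is that fewer results can be called significant. Naming one deciding test keeps that test at 0.05 and leaves d = 0.74 unchanged. Bonferroni over four, six or eight tests would instead set the per-test level at 0.05/4 = 0.0125, 0.05/6 = 0.0083 or 0.05/8 = 0.00625. The detectable effect would rise to d = 0.89, 0.93 or 0.95, and power at d = 0.74 would fall from 80% to about 61%, 56% or 52%.

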9.0 Procedures Involved*

9.1 Study Design

We propose a single center randomized trial of a positive psychology intervention (PATH) versus usual care in 70 patients with hematologic malignancies undergoing HSCT. Participants will be randomized equally to the two arms using randomized permuted blocks of sizes two and four, with randomization stratified by presence/absence of GVHD. As allogeneic transplant recipients with GVHD have significantly different courses of recovery, QOL, and function post-transplant, we will stratify by GVHD status to ensure adequate and balanced representation between the two study groups.

PROTOCOL TITLE: Randomized Trial of a Positive Psychology Intervention for Patients with Hematologic Malignancies Undergoing Hematopoietic Stem Cell Transplantation

The goals of this study are to assess the feasibility, acceptability and preliminary efficacy of this novel 9-session, weekly PP-based intervention for HSCT patients.

Patients will be contacted via telephone or in person at a routine clinic visit close to their routine 70-80-day post-transplant visit for eligibility determination. Interested patients will be screened based on the inclusion/exclusion criteria and provided a study information sheet via mail, e-mail or in-person at a routine clinic visit. Consent procedures would be completed in-person at a routine clinic visit or verbally over the phone approximately seven days after study information is provided.

Upon consent to participate in the study, participants will be given an electronic pill bottle (MEMS Cap) [to be used from the time of baseline assessment completion through the entire duration of the intervention], and an accelerometer to be worn for 7 days prior to the initiation of the intervention. Between the 85-95-day point, all participants will also complete baseline questionnaires either in person, over phone or via a REDCap survey link to participants. Additionally, participants randomized to the intervention group will be given an intervention manual with 9 weekly PP exercises.

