- **Disease Worsening/Mortality:** Given the burden of treatment for patients with hematologic malignancies undergoing HSCT, we do anticipate that a minority of participants will be unable to complete the study protocol due to deteriorating health or death. Our research team has given considerable thought to this concern and adequately powered the study to account for missing data. Based on prior work, we anticipate a 15% attrition rate. The study CRCs will maintain detailed records for patient attrition due to disease-related factors.
- **Refusal to Participate:** Participants who are successfully recruited into the study but later refuse to participate in subsequent intervention sessions pose a threat to the proposed study. In our previous trial, our refusal to participate rate after study enrollment was quite low and all participants who started the intervention actually completed the all the intervention sessions. Again, the CRCs will maintain detailed records for patient refusals.
- **Loss of Contact:** Another source of attrition involves those subjects who are successfully recruited into the study but who cannot be located for subsequent follow-up assessments. Like attrition due to subject refusal, attrition due to loss of contact poses a threat to the proposed study. We do not anticipate this to be a major

PROTOCOL TITLE: Randomized Trial of a Positive Psychology Intervention for Patients with Hematologic Malignancies Undergoing Hematopoietic Stem Cell Transplantation

issue for the proposed study given the intensive and frequent outpatient follow-up visits for patients with hematologic malignancies during the first six months post-HSCT.

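### The missing-data rule lets the stated reason for dropout steer the between-group model towards a weakly identified fallback, without saying which result is the main one

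*Combined protocol and SAP*

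**What the plan says.** Under Aim 2, Section 10.1 specifies a random-intercept model with categorical time (baseline, week 9, week 18), group and their interaction. The interaction coefficients are the stated focus, and the resulting effect sizes go into a power calculation for a full-scale trial. GVHD status, which stratifies the randomisation in Section 9.1, is not among the listed model terms.

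The Missing Data paragraph of Section 10.1 commits to intention-to-treat with everyone randomised and to sensitivity analyses under different missing-data assumptions. It then sets a condition. If the missing data seem to be missing at random, the mixed models are said to be unbiased. But "if we find that participants do not complete the study because of disease worsening, suggesting missing data are not random", then "we will employ pattern mixture modeling or joint modeling approaches", together with a further sensitivity analysis. The paragraph gives no proportion or test for the condition, no choice between the two model classes and no identifying restrictions. It does not say which estimate would be reported as the main one.

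On how much dropout to expect, Section 10.2 says "we anticipate 15% of enrolled participants will be unable to complete the intervention due to medical complications and mortality". Section 11.0, in its item on worsening disease and death, says "Based on prior work, we anticipate a 15% attrition rate". The neighbouring items describe refusal after enrolment and loss of contact as minor sources. Section 13.0 expects worsening and deaths throughout the study.

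**The concern.** The rule asks the analyst to decide from the data whether missingness is random. Observed data cannot separate missing at random from missing not at random. The proxy offered, that people left because their disease worsened, does not do it either. If worsening shows in the scores already returned, or in GVHD status, the dropout can be missing at random given those variables. A likelihood-based mixed model that contains them then remains valid.

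The branch written as the exception also describes the dropout the plan predicts. Following the rule would move the between-group analysis towards models that about five dropouts per arm can inform only weakly, under restrictions not set in advance. At stake are the Aim 2 time-by-group estimates and, through them, one input to the next trial's sample size. The rule refers to the mixed models in general, so the Aim 3 activity and adherence models appear to fall under it too.

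**Working it through.** **Inputs.** Section 10.2: "we will enroll 70 participants (35 in the [PATH] PP arm"; Section 9.1: "Participants will be randomized equally to the two arms"; hence 35 per arm. Attrition is 15% (Sections 10.2 and 11.0). Section 10.2 aims to "target having at least 30 PP participants who complete the intervention" and later refers to "this sample of 30 completers in each group".

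**1. The plan's own figure.** 35 × (1 − 0.15) = 29.75, about 30 completers per arm. In reverse, 30 / 0.85 = 35.3, which rounds up to 36 against the stated 35. The plan's figure is reproduced to within one participant.

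**2. Expected dropouts.** 0.15 × 35 = 5.25 per arm (central 95% binomial range 2 to 10). 0.15 × 70 = 10.5 overall (5 to 17).

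**3. How likely is the fallback?** Read literally, one disease-related dropout is enough: P(at least one of 70) = 1 − (1 − rate)^70.

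| Assumed rate of disease-related dropout | P(at least one of 70) |
|---|---|
| 15% (the plan's figure) | 0.99999 |
| 7.5% (assumption: half of it) | 0.996 |
| 5% (assumption: a third of it) | 0.972 |

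The plan states no threshold. If the team applied one, the probability at a 15% rate would be:

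| Assumed threshold | Count of 70 | P(reached) |
|---|---|---|
| 5% | 4 or more | 0.996 |
| 10% | 7 or more | 0.916 |
| 15% | 11 or more | 0.484 |
| 20% | 14 or more | 0.157 |

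**4. What a pattern-mixture model would have to work with.** Two follow-up visits give two monotone dropout patterns: leaving before week 9, and leaving between weeks 9 and 18. The documents give no split, so these are assumptions:

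- Even split: 5.25 / 2 = 2.6 per pattern per arm. The chance that at least one arm has 0 or 1 participants in a given pattern is 0.44.
- 25/75 split: 1.3 and 3.9 per arm.

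The first pattern has baseline data only, so neither its week-9 nor its week-18 group effect can be estimated without outside restrictions. The second lacks week 18. Its week-9 contrast, with 3 per arm, has a 95% half-width of t(0.975, 4 df) × √(2/3) = 2.776 × 0.816 = 2.27 SD. The plan calls 0.8 SD a large effect.

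**5. What a joint model would have.** It uses the longitudinal data of all 70 participants. The roughly 10.5 dropouts limit its dropout part and the parameter linking dropout to the outcome.

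**6. Size of the stake (illustration only).** Lowering the unseen scores of 15% of one arm by δ SD moves that arm's mean by 0.15 × δ. For δ = 0.5 this is 0.075 SD. An equal shift in both arms with equal dropout cancels. If it applied to PATH alone and the effect were d = 0.5, the estimate would become 0.425. Required sample size varies as 1/d², so it would rise by a factor of (0.5 / 0.425)² = 1.38. Neither δ = 0.5 nor d = 0.5 is predicted by the documents.

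**The case against.** The team has several fair replies.

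- **A reader might infer that the mixed model is abandoned.** The text does not say so. Aim 2 names the interaction coefficients as the focus without any condition, and the fallback could be meant as an additional analysis. This stands. The defect is that the paragraph leaves the main result undetermined, not that it certainly replaces it.
- **A reader might infer that no sensitivity analysis is otherwise planned.** That is wrong: sensitivity analyses are promised unconditionally just before the rule. Only their content is missing.
- **A reader might call the trigger almost certain.** That needs the literal, no-threshold reading. It also equates stopping the intervention (the 15% of Section 10.2) with leaving the study. Section 11.0 supports the link by applying 15% to completing the study protocol and to missing data. Even so, participants who stop sessions can still answer by phone, on paper, in clinic or online. Very likely on a literal reading is as far as the documents go.
- **A reader might say five dropouts per arm must identify a joint model.** Not so, as step 5 shows. The difficulty is sharpest for pattern-mixture models.
- **A reader might infer that the trial's conclusion is at risk.** Aim 2 is secondary, and Section 10.2 offers only tentative effect sizes. The next trial's sample size will also be checked against a clinically meaningful difference and the literature.
- **Deaths are partly covered.** Section 11.0 provides for deaths listed by cause and for records of disease-related attrition. These are monitoring reports; Section 10.1 does not separate deaths from unreturned questionnaires in the analysis.

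**Conclusion.** The point holds in a limited form and is a cheap improvement. The rule conditions the analysis on a judgement that observed data cannot support, and its proxy matches the dropout the plan predicts: about 5 per arm, provided those who stop the intervention also stop returning questionnaires. If the fallback were used, pattern-specific effects would depend on restrictions the plan does not state, or the dropout part of a joint model would rest on about 10 events. Because no main result is named, the reason recorded for dropout could steer the effect sizes carried into planning the next trial. The dropout counts assume the plan's 15% rate in both arms; the trigger probabilities also assume independent dropout. The documents do not allow the actual change in any estimate to be calculated. The primary feasibility result does not depend on this rule.

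**What to change.** In Section 10.1:

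1. State that the linear mixed model already described, with the GVHD randomisation stratum added, is the main between-group analysis whatever the reasons for dropout.
2. Replace the conditional rule with one pre-specified missing-not-at-random sensitivity analysis that is always run. Delta-adjusted imputation over a range of shifts, varied by arm, would serve. It is itself a pattern-mixture method, so it keeps the team's concern about disease-related dropout while making the untestable assumption explicit. The team should set and justify the range before seeing outcome data; the documents give no basis for particular values.
3. Report deaths by arm separately from missing questionnaires.

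The cost is a few sentences in the plan and one extra analysis run, with no new data, participants or procedures. The joint model is no longer a candidate for the main analysis.

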1.2 Specific Aims/Objectives

#1 (Feasibility; Primary Aim): To determine the feasibility and acceptability of the PATH intervention in patients with hematologic malignancy undergoing HSCT.

PROTOCOL TITLE: Randomized Trial of a Positive Psychology Intervention for Patients with Hematologic Malignancies Undergoing Hematopoietic Stem Cell Transplantation

Hypothesis: The PATH intervention will be deemed feasible with >75% of participants randomized to the intervention arm completing ≥ 6/9 positive psychology exercises. The PATH intervention will be deemed acceptable with mean ease and utility scores of each exercise being ≥ 7/10.

#2 (Effects on Patient-Reported Outcomes): To assess the preliminary efficacy of the PATH intervention on psychological (e.g., depression, anxiety, optimism, positive affect), QOL, and functional outcomes compared to the usual care condition.

Hypothesis: Patients randomized to the PATH intervention will have improved PPWB (e.g., optimism, positive affect, gratitude), mood (e.g., depression and anxiety), and QOL compared to those in the usual care condition.

#3 (Effects on Health Behaviors): To examine the impact of the PATH intervention on behavioral outcomes (e.g., medication adherence, physical activity) compared to those in the usual care condition.

Hypothesis: Patients randomized to the PATH intervention will have improved behavioral outcomes (e.g., medication adherence, physical activity) compared to those in the usual care condition.

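### The 95% power quoted for the primary feasibility aim is against 50% completion, but the declared criterion is above 75%; at the plan's own 80% rate the chance of meeting that criterion is about 75%

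*Combined protocol and SAP*

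**What the plan says.** Section 1.2, aim 1, sets the criterion: "The PATH intervention will be deemed feasible with >75% of participants randomized to the intervention arm completing ≥ 6/9 positive psychology exercises". Section 10.1, Specific Aim 1, repeats the 75% threshold, again out of nine, with a different denominator: "we define feasibility as >75% of enrolled participants who start the intervention completing at least 6 of the" […]. Section 10.1 also says how it is assessed: "We will estimate the feasibility using the proportion who meet the criteria, and we will place an exact 95% binomial confidence interval around the proportion". No hypothesis test is planned for this endpoint.

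Section 10.2 gives the sample-size argument for the same aim. It starts from an assumed rate: "in prior trials, approximately 80% of participants have completed 6 of 9 PP exercises". At that rate and a PATH sample of 30, it reports power of 95% for a binomial test at the two-sided 5% level. The stated purpose of the test is as follows: "to demonstrate that the proportion who complete > 6 of 9 PP sessions is larger than 50% (i.e., a majority"). On arm size, "we will enroll 70 participants (35 in the [PATH] PP arm) to target having at least 30 PP participants who complete the intervention", after allowing for 15% of enrolled participants being unable to complete because of medical complications or death.

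**The concern.** The only power figure offered for the primary aim refers to a benchmark of 50%. That benchmark appears in neither statement of the criterion nor in the planned analysis. The assumed true rate of 80% is 30 points above 50% but only 5 points above the 75% threshold, so the two probabilities must differ widely.

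The same data can also give opposite answers under the two benchmarks. With 30 participants, 21 completers (70%) or 22 (73%) would reject 50% in an exact test but fail the 75% criterion. If section 10.2 does not say which count passes, a near miss could later be read against 50%. Section 10.2 disclaims power only for group differences in psychological, quality-of-life and behavioral outcomes, not for feasibility, so readers have reason to rely on the feasibility figure.

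**Working it through.** **Inputs.** Threshold: observed proportion strictly above 0.75 (sections 1.2 and 10.1). Assumed true rate 0.80, null 0.50, two-sided alpha 0.05, n = 30, PATH arm 35, attrition 15% (all section 10.2).

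**Step 1: reproduce the stated 95%.** One-sample test of p0 = 0.50 against p1 = 0.80 with n = 30.

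- Normal approximation: power = Φ[(p1 − p0 − 1.96·√(p0(1−p0)/n)) / √(p1(1−p1)/n)] = Φ[(0.30 − 1.96 × 0.0913) / 0.0730] = Φ(1.66) = 95.1%.
- Exact binomial: reject at 21 or more of 30 (upper-tail probability under 50% is 0.021; at 20 or more it is 0.049, above 0.025). P(X ≥ 21 | 30, 0.80) = 93.9%.

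The stated figure is reproduced.

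**Step 2: minimum passing count under the declared criterion.** For n = 30, 0.75 × 30 = 22.5, so at least 23 (76.7%). For n = 35, 0.75 × 35 = 26.25, so at least 27 (77.1%).

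**Step 3: chance of meeting it.** P(X ≥ r | n, p) from the binomial distribution:

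| True rate | n = 30, at least 23 | n = 35, at least 27 |
|---|---|---|
| 70% | 28% | 23% |
| 75% | 51% | 47% |
| 80% | 76.1% | 74.5% |
| 85% | 93% | 93% |
| 90% | 99% | 99% |

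At 80%, the chance of missing the criterion is 24% (n = 30) or 25% (n = 35). Because counts are whole numbers, the chance of passing at 80% moves unevenly with n: from 68% at n = 28 to 80% at n = 33, over the range 28 to 35.

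**Step 4: how often the two benchmarks disagree.** At n = 30 and a true 80%, P(X = 21 or 22) = 93.9% − 76.1% = 18%.

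**Step 5: effect of the denominator.** Section 1.2 counts everyone randomized to PATH, section 10.1 counts those who start, and section 10.2 uses the 30 expected to complete. Suppose all 35 randomized are counted, the 15% unable to complete are failures, and 80% applies to the rest. This is an assumption; the documents do not say whether the cited 80% already includes drop-outs. The overall rate is then 0.85 × 0.80 = 0.68, and P(X ≥ 27 | 35, 0.68) = 16%.

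**Step 6: precision at a bare pass.** The exact 95% interval is 57.7% to 90.1% for 23/30 and 59.9% to 89.6% for 27/35.

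**The case against.** Several points on the other side are sound.

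- A reader might infer that the 95% is miscalculated. It is not; step 1 reproduces it. Section 10.2 also names its 50% null openly and does not claim 95% power for the 75% criterion. What is missing is the operating characteristic of the declared rule.
- A reader might treat the criterion as a go/no-go rule and a pass at a true 70% as a false go. The documents do not support this. Section 10.1 plans an estimate with an interval, no true rate is named as unacceptable, and Table 1 in section 7.0 schedules the multi-site grant proposal without making it conditional on the result.
- A reader might require the lower confidence limit to exceed 75%. That would need 28/30 or 32/35, with a chance of only 4.4% or 6.1% at a true 80%. The plan does not ask for it: the criterion is on the observed proportion.
- The true rate may exceed 80%. Section 9.7 reports 100% completion in the proof-of-concept trial in this population, and at 85% the chance of passing is already 93%. This stands as a reason to show a range. It does not rescue the 95%, because section 10.2 itself adopts 80%. Section 9.7 also cites completion as low as 64% in other medical populations. That figure is for exercises, so it may not translate directly, but a 64% participant rate would give only 10% (n = 30) or 7% (n = 35).
- A single replacement figure of 75% would be unsafe while the denominator is open. This stands, and the fix is made conditional on it.

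**Conclusion.** The point holds as a mismatch between the primary criterion and the power statement offered for it, not as an arithmetic error. At the plan's own 80% rate, the chance of meeting the declared criterion is about 76% (30 participants) or 75% (35), roughly 20 points below the 95% a reader might carry over to it. These figures assume independent participants and that 80% applies to whichever denominator is used. If attrition counts as failure on top of that 80%, the chance could be about 16%.

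The trial is not invalidated: the estimate and its exact interval remain informative. Nothing here shows that 70 participants is the wrong number for a pilot. Nor do the documents support lowering the criterion to 50% to match the power statement, since section 10.1 ties the 75% threshold to earlier feasibility trials.

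**What to change.** Revise the feasibility paragraph of section 10.2.

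1. State which denominator applies, all randomized to PATH or those who start, and use it in sections 1.2, 10.1 and 10.2. In the same edit, reconcile the count: section 10.2 writes more than 6 of 9, while the other two sections use at least 6.
2. Replace the 50% power statement, or keep it labelled as a secondary benchmark, and add the operating characteristics of the 75% criterion: the minimum passing count (23/30 or 27/35) and the chance of reaching it at true rates of 70%, 75%, 80% and 85%. These are 28%, 51%, 76% and 93% for n = 30, and 23%, 47%, 75% and 93% for n = 35. If starters are the denominator, their number is not fixed in advance, so add the 68% to 80% range for n from 28 to 35 at a true 80%.
3. If all randomized are counted, say whether the assumed 80% already includes those unable to complete. If it does not, show the 68% scenario and its 16% chance.

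Keep the criterion above 75% and the sample size of 70. The change needs no extra patients, data or analyses. Its cost is one paragraph, the matching edits to the definition, and a less favourable stated figure.
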